6.3 POST-STUDY ACCESS

At the end of the study period, TG therapeutics, Inc. will not continue to supply study drug to subjects/investigators unless the Sponsor-Investigator chooses to extend their study and TG Therapeutics, Inc. provides written approval. The investigator is responsible to ensure that the subject receives appropriate standard of care or other appropriate treatment in the independent medical judgment of the Investigator to treat the condition under study.

7 STUDY PROCEDURES AND SCHEDULE

7.1 STUDY PROCEDURES /EVALUATIONS

PET/CT: A scan is done at baseline as part of the initial staging evaluation. PET/CT scan performed within 42 days prior to registration. PET scans, in conjunction with diagnostic-quality CT scans, will be obtained in this study. PET-CT scans should include skull-base to mid-thigh. Full-body PET-CT scan should be performed when clinically appropriate.

CT scans with oral and IV contrast should include neck, chest, abdomen, and pelvic scans. In patients for whom contrast is contraindicated, (e.g., patients with contrast allergy or impaired renal clearance or patient denial), CT or combined PET-CT scans without contrast are permitted so long as they permit consistent and precise measurement of target lesions during the study treatment period.

For Follicular lymphoma patients: All response assessments will be PET/CT based.

For Marginal Zone lymphoma patients: If Baseline PET/CT does NOT demonstrate uniformly

FDG avid lesions subsequent assessments on the study will be done with CT scans of the neck, chest, abdomen and pelvic scan with contrast ONLY. If Baseline PET/CT demonstrates uniformly FDG avid lesions subsequent assessments on the study will be done with PET/CT scans.

A PET/CT will be done 8 weeks post completion of induction therapy (EOI PET/CT) with single agent ublituximab.

Patients who achieve a CR (Lugano response Criteria for NHL (Cheson 2014) will be followed by PET/CT done at the 6 months, 12 months, 18 months and 24 months post EOI (end of induction treatment) PET/CT. After this, imaging will be performed at the discretion of the investigator.

Patients who do not achieve a CR will initiate therapy with combination umbralisib and ublituximab. On this combination treatment, a PET/CT will be done prior to Cycle 4, cycle 8 and Cycle 12. Patients who achieve a CR during these time points will continue on combination therapy for the entirety of the 12 cycles course of treatment.

A PET/CT will be done 12 weeks post completion of combination therapy (EOT PET/CT).

Patients on the combination treatment who are post completion of 12 cycles of therapy will enter the follow up period in which a PET/CT will be done at the 6 months, 12 months, 18 months and 24 months post EOT PET/CT.

Bone Marrow Biopsy: Patients with FL and MZL must have a bone marrow biopsy performed within 6 months prior to registration. For patients with FL, response assessment of bone marrow involvement by lymphoma will be by PET scan only and bone marrow aspirates and biopsies will not be required for assessment of disease response.. For patients with MZL a restaging bone marrow biopsy will be done 8 weeks post completion of induction therapy with single agent ublituximab if a staging bone marrow biopsy was previously positive. On the combination arm, a bone marrow biopsy (if initially involved) will be done 12 weeks post completion of 12 cycles of therapy if a staging bone marrow biopsy was previously positive.

Post-Trial Assessments: Patients who go off study treatment at any time during the trial will complete end of treatment assessments per section 7.3. For all patients, drug-related SAEs and AEs will be followed until baseline or \leq grade 1 levels for a total of 30 days. Patients who responded or maintained stable disease during the study will be followed for date of disease progression. Patients may refuse to participate in the post-trial assessments.

Clinical Evaluations: Patients should be seen and evaluated by provider as follows:

Single agent induction therapy: Day 1, Day 8, Day 15, Day 22, 4 weeks and 8 weeks post completion of therapy.

Patients achieving CR to single agent therapy: Will be evaluated in clinic every 3 months for 2 years.

Patients not achieving a CR: Will start Combination therapy.

Combination therapy: Patients will be evaluated on Day 1, Day 8 and Day 15 of C1, and on Day 1 and Day 15 of C2; subsequently, they will be evaluated on Day 1 for cycles 3-12.

After completion of combination therapy, patients will be evaluated in clinic 4 weeks post completion of therapy, 12 weeks post completion of therapy, and then every 3 months for 2 years and every 6 months for years 2 through 5.

Patients should be seen and evaluated by physician no less than one time every 16 weeks (4 cycles).

7.1.1 RESPONSE ASSESSMENT

The timing of PET/CT and Bone marrow biopsy on each single agent and combination therapy arms of the trial have been outlined in 7.1.

Patients with a global deterioration of health status requiring permanent discontinuation of study treatment (taken off study) without objective evidence of disease progression and without evidence of other causes to attribute to deteriorating health will be counted as progressive disease. Every effort should be made to document the objective progression even after discontinuation of treatment. Deaths of unknown cause and those related to malignancy or treatment-related toxicity will be counted as treatment failure.

Patients will be analyzed with respect to imaging-based CR, overall survival (OS) and progression-free survival (PFS). Overall survival is defined as time from the first chemotherapy administered on trial until death from any cause. For subjects who are still alive at the time of the study analysis or who are lost to follow-up, survival will be censored at the last recorded date that the subject was known to be alive. Progression-free survival is defined as time from therapy until relapse, progression, or death from any cause. Response will be determined by the principal investigator or the co-principal investigators.

Definitions for clinical response for patients with lymphoma are from the Lugano response criteria (Cheson et al. 2014).³⁴ Response assessment will be performed by treating provider, and will be performed at the University of Colorado.

Definitions of Tumor Response and Progression

Responses will be categorized as complete response (CR), partial response (PR), stable disease (SD), or progressive disease (PD). In addition, a response category of nonevaluable (NE) is provided for situations in which there is inadequate information to otherwise categorize response status.

The screening measurement will be taken as a reference for determinations of response. The nadir measurement will be taken as a reference for PD; this measurement constitutes the smallest measurement recorded, including the screening measurement if this is the smallest measurement. For FDG-avid tumors, metabolic criteria for response by PET-CT will take precedence over anatomic criteria for response by contrast CT when assessing CR.

For patients staged with PET-CT, focal uptake in nodal and extranodal sites that is in keeping with lymphoma, according to the distribution and/or CT characteristics, is considered involvement with lymphoma, including spleen, liver, bone, thyroid, and so on. For patients staged with CT, up to six of the largest target nodes, nodal masses, or other lymphomatous lesions that are measurable in two diameters (longest diameter [LD_i] and shortest diameter) should be identified from different body regions representative of the patient's overall disease burden and include mediastinal and retroperitoneal disease, if involved. A measurable node must have an LD_i greater than 1.5 cm. Measurable extranodal disease (eg, hepatic nodules) may be included in the six representative, measured lesions. A measurable extranodal lesion should have an LD_i greater than 1.0 cm. All other lesions (including nodal, extranodal, and assessable disease) should be followed as nonmeasured disease (eg, cutaneous, GI, bone, spleen, liver, kidneys, pleural or pericardial effusions, ascites). In patients in whom a discordant histology or malignant transformation is suspected, a PET-CT may identify the optimal site to biopsy for confirmation.

Revised Criteria for Response Assessment: Lugano Classification (cont.)

Response	Site	PET-CT-Based Response	CT-Based Response
Complete		Complete metabolic response	Complete radiologic response (all of the following)
	Lymph nodes and extralymphatic sites	
Score 1, 2, or 3^a with or without a residual mass on 5PS^b
 
It is recognized that in Waldeyer's ring or extranodal sites with high physiologic uptake or with activation within spleen or marrow (e.g., with chemotherapy or myeloid colony-stimulating factors), uptake may be greater than normal mediastinum and/or liver. In this circumstance, complete metabolic response may be inferred if uptake at sites of initial involvement is no greater than surrounding normal tissue even if the tissue has high physiologic uptake
	
Target nodes/nodal masses must regress to ≤ 1.5 cm in LD_i
 
No extralymphatic sites of disease

	Nonmeasured lesion	Not applicable	Absent
	Organ enlargement	Not applicable	Rgress to normal
	New lesions	None	None
Partial		Partial metabolic response	Partial remission (all of the following)
	Lymph nodes and extralymphatic sites	
Score of 4 or 5^b with reduced uptake compared with baseline and residual mass(es) of any size
 
At interim, these findings suggest responding disease
 
At end of treatment, these findings indicate residual disease
	
$\geq 50\%$ decrease in SPD of up to 6 target measureable nodes and extranodal sites
 
When a lesion is too small to measure on CT, assign 5 mm x 5 mm as the default value
 
When no longer visible, 0 x 0 mm
 
For a node $> 5\text{mm} \times 5\text{ mm}$, but smaller than normal, use actual measurement for calculation

Revised Criteria for Response Assessment: Lugano Classification (cont.)

Response	Site	PET-CT-Based Response	CT-Based Response
Partial (cont.)	Nonmeasured lesions	Not applicable	Absent/normal, regressed, but no increase
	Organ enlargement	Not applicable	Spleen must have regressed by $\geq 50\%$ in length beyond normal.
	New lesions	None	None
	Bone marrow	Residual uptake higher than uptake in normal marrow but reduced compared with baseline (diffuse uptake compatible with reactive changes from chemotherapy allowed). If there are persistent focal changes in the marrow in the context of a nodal response, consideration should be given to further evaluation with MRI or biopsy or an interval scan.	Not applicable
No response or Stable Disease		No metabolic response	Stable disease
	Target nodes/nodal masses, extranodal lesions	Score 4 or 5 ^b with no significant change in FDG uptake from baseline at interim or end of treatment	$> 50\%$ decrease from baseline in SPD for up to 6 dominant, measurable nodes and extranodal sites; no criteria for progressive disease are met.
	Nonmeasured lesions	Not applicable	No increase consistent with progression
	Organ enlargement	Not applicable	No increase consistent with progression
	New lesions	None	None
	Bone marrow	No change from baseline	Not applicable

Revised Criteria for Response Assessment: Lugano Classification (cont.)

Response	Site	PET-CT- Based Response	CT-Based Response
Progressive Disease		Progressive metabolic disease	Progressive disease (requires at least 1 of the following)
	Individual target nodes/nodal lesions	Score 4 or 5 ^b with an increase in intensity of uptake from baseline and/or new FDG-avid foci consistent with lymphoma at interim or end-of-treatment assessment	PPD progression: An individual node/lesion must be abnormal with: 
 • LD_i> 1.5 cm AND • Increase by >= 50% from PPD nadir AND • An increase in LD_i or SD_i from nadir • 0.5 cm for lesions <= 2cm • 1.0 cm for lesions > 2cm
	Extranodal lesions		
	Nonmeasured lesions	None	New or clear progression of preexisting nonmeasured lesions
	Organ enlargement		In the setting of splenomegaly, the splenic length must increase by > 50% of the extent of its prior increase beyond baseline (e.g., 15-cm spleen must increase to > 16 cm). If no prior splenomegaly, must increase by at least 2 cm from baseline. New or recurrent splenomegaly
	New lesions	New FDG-avid foci consistent with lymphoma rather than another etiology (e.g., infection, inflammation). If uncertain regarding etiology of new lesions, biopsy or interval scan may be considered.	Regrowth of previously resolved lesions A new node > 1.5 cm in any axis A new extranodal site > 1.0 cm in any axis; if < 1.0 cm in any axis, its presence must be unequivocal and must be attributable to lymphoma Assessable disease of any size unequivocally attributable to lymphoma.
	Bone marrow	New or recurrent FDG-avid foci	New or recurrent involvement

5-PS = 5-point scale; CT = computed tomography; FDG = fluorodeoxyglucose; IHC = immunohistochemistry; LD_i = longest transverse diameter of a lesion; MRI = magnetic resonance imaging; PET = positron emission tomography (scan); PPD = cross product of the LD_i and perpendicular diameter; SD_i = shortest axis perpendicular to the LD_i; SPD = sum of the product of the perpendicular diameters for multiple lesions.

^a A score of 3 in many patients indicates a good prognosis with standard treatment, especially if at the time of an interim scan. However, in trials involving PET where de-escalation is investigated, it may be preferable to consider a score of 3 as inadequate response (to avoid under treatment).

^b PET 5PS: 1, no uptake above background; 2, uptake <= mediastinum; 3, uptake > mediastinum but < liver; 4, uptake moderately liver; 5, uptake markedly higher than liver and/or new lesions; X, new areas of uptake unlikely to be related to lymphoma.

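### As printed, the CT-based stable-disease cut-off (> 50% decrease in SPD) lies inside the partial-remission range, so a CT-assessed patient with less than a 50% decrease who is neither CR nor PD fits no row

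*Combined protocol and SAP*

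**What the plan says.** Section 7.1.1 sets out four response classes: "Responses will be categorized as complete response (CR), partial response (PR), stable disease (SD), or progressive disease (PD"). It adds a nonevaluable class for cases where the information is inadequate. The working definitions are in the Lugano table of that section. Its CT-based column reads as follows.

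- **Complete:** "Target nodes/nodal masses must regress to" 1.5 cm or less in longest diameter (LDi), with further conditions on other sites.
- **Partial:** headed "Partial remission (all of the following"), the first condition being a ≥ 50% "decrease in SPD of up to 6 target measureable nodes and extranodal sites". Conditions on nonmeasured lesions, spleen and new lesions follow.
- **Stable:** a > 50% "decrease from baseline in SPD for up to 6 dominant, measurable nodes and extranodal sites; no criteria for progressive disease are met". With its sign, and with stray markup left by text extraction, the opening of this cell reads "> 50\%$ decrease from baseline in SPD".
- **Progressive:** for a target node, LDi above 1.5 cm, a product of diameters (PPD) up by ≥ "50% from PPD nadir AND" a minimum rise in a diameter. Other forms of progression also count.

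Section 7.1 says who is read by this column: MZL patients whose baseline PET/CT does not show uniformly FDG-avid lesions have CT only from then on. Follicular lymphoma patients are always assessed by PET/CT.

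The SD rate is an exploratory objective (section 3) and is to be summarized for the FL and MZL cohorts (section 10.4.10). ORR is CR plus PR (section 10.2) and is descriptive (section 10.4.3).

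**The concern.** Stable disease should take the patients who have neither responded nor progressed. With the printed sign it asks for a larger shrinkage than partial remission does. Two things follow from a literal reading.

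- **Gap.** A measured patient below a 50% decrease who is neither CR nor PD belongs to no class. The nonevaluable class does not take this patient, because the imaging is adequate.
- **Overlap.** A non-CR patient above a 50% decrease who meets the other PR conditions satisfies both the PR and the SD cells. The table states no order of precedence.

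At stake is the SD rate among CT-only MZL patients. These would have to be classified by a convention that the protocol does not state, or left out of the tabulation.

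**Working it through.** The plan gives no figure of its own to reproduce on this point. The check runs cases through the printed rules.

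**Inputs** (CT-based column, section 7.1.1). Let d be the percent decrease in SPD from baseline. For one target node, SPD is the product of its two diameters, so d = 100 x (baseline product − current product) / baseline product. All other CR and PR conditions are taken as met, and baseline is taken as the nadir.

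- CR: LDi ≤ 1.5 cm
- PR: d ≥ 50
- PD: LDi > 1.5 cm, product up by ≥ 50% from nadir, and the required diameter rise
- SD as printed: d > 50 and not PD
- SD if the sign is <: d < 50 and not PD

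**Cut-offs alone, patient not CR and not PD.** As printed, SPD changes of +40%, +10%, 0, −10%, −30% and −49.9% match neither PR nor SD. A change of −50% matches PR only. Changes of −50.1%, −60% and −80% match both. With SD at d < 50, the first six are SD and the last four are PR, one class each.

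**Single-node cases.**

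| Case | Node (cm) | Product (cm²) | d | As printed | With SD at < 50% |
|---|---|---|---|---|---|
| A | 3.0 x 2.0, unchanged | 6.0 to 6.0 | 0 | no row | SD |
| B | 3.0 x 2.0 to 2.5 x 1.7 | 6.0 to 4.25 | 1.75/6.0 = 29.2% | no row | SD |
| C | 2.0 x 1.5 to 1.5 x 1.2 | 3.0 to 1.8 | 1.2/3.0 = 40% | CR | CR, and meets the SD cell |
| D | 4.0 x 3.0 to 2.4 x 1.8 | 12.0 to 4.32 | 7.68/12.0 = 64% | PR and SD | PR |
| E | 4.0 x 3.0 to 3.0 x 2.0 | 12.0 to 6.0 | 6.0/12.0 = 50% | PR | PR |
| F | 3.0 x 2.0 to 3.3 x 2.4 | 6.0 to 7.92 | −1.92/6.0 = −32% | no row | SD |

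Case C shows that CR takes some patients below a 50% decrease. Cases A, B and F show that it does not take all of them. Case F grows by 32%, short of the 50% needed for PD.

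**What the sign alone does not settle.** PR needs all its conditions, including spleen regression of at least 50% of the length beyond normal. The table's own example, "15-cm spleen must increase to > 16 cm", implies a 13 cm reference: an increase of more than 1 cm is half of the 2 cm excess, and 15 − 2 = 13. A spleen going from 17 to 16 cm loses 1 of 4 cm of excess, or 25%. With d = 60% that patient is not PR and not PD. With SD at < 50% and nothing else, the patient has no row.

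**The case against.** The strongest objection is that everything turns on one symbol in a table read from a PDF by a program. Comparators in this table are not fully reliable: the footnote on the five-point scale has lost the one for score 4. The partial and stable rows contain no < sign that would show such signs were read correctly there. On the other side, ≥ prints correctly in the same column, and < prints later in the same table and in the creatinine criterion of section 5.1. A lost sign is also a different failure from a reversed one. This makes a true > plausible but does not prove it. The objection stands to the extent that the source must be checked first.

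The second objection is context. The row label pairs non-response with stable disease, its PET-based cell describes no significant change in uptake, and the section names the Lugano criteria as its source. A sensible reader would code an unchanged node as SD and a 64% shrinkage meeting all PR conditions as PR. This is largely right, and it makes the practical risk small. It does not make the printed cell correct: the table is the working rule, response is judged by the treating provider, and nowhere is SD said to be the remainder.

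A reader might go further and infer that ORR will be distorted. That would require a patient who meets every PR condition to be coded SD on the overlap, which the row label argues against. A reader might also infer harm to the primary result. The CT-based CR cell is separate and contains no SPD cut-off, and the test of 30% against 50% with 24 patients uses only CR. The move to combination therapy depends only on CR or not CR.

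**Conclusion.** The point holds for the text as printed and is minor. The CT-based SD range is contained in the PR range, and every patient who is neither CR nor PD with less than a 50% decrease is left without a row. The direct effect is confined to the exploratory SD rate in MZL patients followed by CT only. It cannot be quantified, because the documents do not say how many such patients are expected.

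This is best read as a typographical error in an operative rule. The documents do not support reading it as a deliberate analysis choice.

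Confidence is medium. The logic needs no outside source, but the conclusion assumes that the > sign is in the source document. If the source reads <, the point falls away.

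**What to change.** 1. Check the sign in the CT-based stable-disease cell against the source document.
2. If it reads >, change the cell to a < 50% decrease from baseline in SPD, keeping the condition that no PD criterion is met. This is the complement of the PR cut-off in the same column. Align the CRF or reader instructions.
3. Optionally, when making that correction, state that the categories are applied in order. SD would go to a patient with adequate imaging who meets neither CR nor all PR conditions, and who is not PD either by the table or by the rule in section 7.1.1 that counts global deterioration as progression. This keeps case C as CR and gives the spleen example a class. Naming the deterioration rule avoids a new conflict with it.

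If the source already reads <, no change is needed for this point. The cost is one symbol, with one optional sentence and the matching CRF or reader text. Sample size and data collection are not affected.

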7.2 LABORATORY PROCEDURES/EVALUATIONS

Local laboratory assessments as specified on the schedule of events table will include the following:

- Hepatitis B virus (HBV) testing will include hepatitis B surface antigen (HBsAg), antibody to the hepatitis B surface antigen (anti-HBs), and antibody to the hepatitis B core antigen (anti-HBc). If a subject is anti-HBc or HBsAg positive, a quantitative polymerase chain reaction test to measure viral DNA load will be performed. Interpretation of this test is described in the **Appendix** section
- Testing for HCV (testing for antibody; if positive then quantitative polymerase chain reaction test to measure viral RNA load).
- HIV testing will be performed per institutional guidelines.
- Testing for CMV, If CMV IgG or IgM is reactive, the subject must be evaluated for the presence of CMV DNA (by PCR).
- Hematology: Complete Blood Count (CBC) with absolute differential, including hematocrit, hemoglobin, white blood cell count (WBC) with differential, and platelet count.
- Chemistry: Comprehensive Metabolic Panel including albumin, alkaline phosphatase, alanine aminotransferase (ALT/SGPT), aspartate transaminase (AST/SGOT), bilirubin (total and direct), calcium, chloride, creatinine, glucose, phosphorous, potassium, sodium, total protein, serum urea/blood urea nitrogen (BUN), LDH, Uric acid.
- Serum beta₂-microglobulin.
- Thyroid function tests will include thyroid stimulating hormone (TSH) and free thyroxine (fT4).
- Calculated creatinine clearance (CrCl) will be estimated using the Cockcroft-Gault formula: CrCl (mL/min) = (140 – age) (weight [kg]) / 72 (serum creatinine [mg/dL]; for females, the formula is multiplied by 0.85 (Cockcroft, 1976).
- Coagulation tests will include prothrombin time, international normalized ratio (INR) and partial thromboplastin time (PTT or activated PTT).
- Urinalysis (a urine dipstick may be used) will include color, appearance, specific gravity, pH, glucose, ketones, blood, bilirubin, and protein. A microscopic examination will be performed if urinalysis result is abnormal.

Pregnancy testing will be performed for females of child-bearing potential. A serum pregnancy test must be done \leq 3 days of starting treatment with single agent ublituximab induction.

